Magnitude and Persistent Health Burden of Child Obesity: In 2018, more than 2 million US children began kindergarten with obesity.¹² The US prevalence of obesity among preschool-aged children increased from 10.1% in 2007-2008 to 13.9% in 2015-2016.³⁰ Low family income and community-level socio-economic deprivation in childhood increase risk for obesity and overweight through adolescence.^{27,31} Rural residency is also associated with higher body mass index (BMI) in childhood and increased odds for childhood obesity.¹²⁻¹⁵ Practitioners and policy makers are cognizant of this disparity, yet rural children remain underrepresented in the literature. The preschool years are a critical period for preventive interventions as rapid gains in BMI during this period lead to early-life obesity and a substantial health burden during childhood, including poor cardiovascular and metabolic health characterized by high blood pressure, dyslipidemia, and insulin resistance,³²⁻³⁵ and other adverse physical health effects such as asthma, obstructive sleep apnea, early maturation, polycystic ovarian syndrome, and non-alcoholic hepatic steatosis.^{36,37} Further, children with obesity report adverse social and emotional health including lower self-esteem and health-related quality of life compared to children with normal weight status.³⁸ These effects during childhood are certainly problematic, but the primary public health burden is the persistence of obesity and duration of adverse effects over time. Longitudinal studies indicate that 60 to 90 percent of preschool-aged children with obesity had persistent obesity into adolescence^{2,3} and adulthood.³⁹ Obesity that persists into adulthood has detrimental effects on health, with a significant impact on population health: based on the prevalence of obesity among children aged 2-19 years in 2016, and assuming no gains in secular trends, 57% of the US population is expected to be obese by age 35 years and will face serious co-morbidities.⁴⁰

Rationale for targeting preschool children: Preschool children are the focal population for this project to respond to a scientific gap in understanding the comparative effectiveness of preventive intervention strategies for preschool-age children. Obesity prevention may have the greatest preventive benefit if begun early in life, before age 2 years, and there is an opportunity to meet patients where they are in clinical well child visits (WCVs) and to extend care in

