Food Insecurity: A majority of childhood obesity prevention studies have targeted populations with low-income but *no interventions* included in recent systematic reviews^{11,43,56-58} have addressed food insecurity, a well-recognized moderator of obesity.⁵⁹⁻⁶² In fact, a 2018 randomized controlled trial of parents of preschool-aged children who received all 5 behavioral targets in home and community settings failed to observe differences in BMI at 3 years follow-up *except among families who were food insecure at baseline*.⁶³ The American Academy of Pediatrics (AAP) issued guidance recommending food insecurity screening; this is a standard social determinant of health indicator in electronic health record (EHR) systems and fully implemented at Geisinger.⁶⁴ Professional guidance highlights the role PCPs play in referring families with food insecurity to community food access resources. Recent studies evaluating the feasibility and acceptability of PCPs in this role has emphasized the importance of providing PCPs with resources to facilitate referrals and ultimately empower parents to improve food security.⁶⁵⁻⁶⁷ Geisinger PCPs have been asked to take action by referring pediatric patients and their parent(s) to Geisinger Wellness' collaborative effort with the Central Pennsylvania Food Bank in response to heightened food insecurity during the COVID-19 pandemic. Specifically, lost wages due to job layoffs and industry closures and limited availability of food due to shortages will strain households that were food insecure while other households will become newly food insecure. Changes in food security will be evaluated as a secondary outcome across all arms.

The specific aims for this project are follows:

1. To compare the effectiveness of WCV vs. PRO WCV vs. PRO WCV + Food Care on obesity prevention for preschool-aged children from rural, lower income households with BMI-for-age and -sex > 50th percentile at baseline.
 - 1a. To examine the effectiveness of the interventions on the change in BMI z-score at 1-year follow-up, and on the percent of children overweight (> 85th percentile BMI-for-age and -sex) and obese (> 95th percentile BMI-for-age and -sex) at 1-year.
 - 1b. To examine the effectiveness of the interventions on a secondary outcome related to parents' perceptions of being involved with the PCP in preventive counseling.

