 - 1c. To examine the effectiveness of the interventions on secondary outcomes related to home and parent factors, including food resource management and household food security.
2. To examine multi-level mediators and moderators of effectiveness of each intervention.
 - 2a. To evaluate whether intervention effectiveness is mediated by parent and PCP attitudes, norms, perceived behavioral control and intention to prevent obesity.
 - 2b. To evaluate whether intervention effectiveness is mediated by child behaviors including nutrition, physical activity, screen time, and sleep.
 - 2c. To explore whether intervention effectiveness is moderated by community, clinic, and home factors. Community factors include socio-economic deprivation, rurality, and parents' perception of their neighborhood. Clinical organizational climate and household income and transportation will be evaluated.
3. To identify factors influencing effective implementation at the parent, PCP, and clinic levels.
 - 3a. To identify factors influencing parent completion and PCP utilization of the PRO measure.
 - 3b. To identify factors influencing use of family-centered preventive counseling.
 - 3c. To identify factors influencing parent utilization of community referrals.

PROCEDURES

Research Design

A cluster-randomized controlled trial will compare effectiveness of the two interventions (Arms 2 and 3) versus control (Arm 1) on the prevention of obesity among preschool-aged children (Aim 1). Geisinger PCPs who conduct WCVs (pediatricians, family or community medicine physicians, nurse practitioners) will represent the units of randomization (i.e., clusters). Families (the eligible child and their parent)—representing the individuals to which study findings will be generalizable—will receive one of the three interventions based on the comparator assignment of the PCP who conducts the child's WCV. Participating PCPs will be randomized into an intervention arm, which entails having changes made to their EHR interface and having these changes impact all preschool-aged children for whom they provide WCV (Arms 2 and 3). The EHR changes are novel to the eligible PCPs. Families will be consented to participate in the study follow-up, but not to the interventions, which require implementation on a system level. Cluster, rather than individual-level, randomization is warranted because of the automated EHR-based intervention, because PCPs cannot be expected to change their standard

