If child is >27 months or <60 months of age, then eligible if greater than or equal to 50th percentile for BMI-for-age and -sex at any visit (WCV, acute, etc) in the prior 15 month period or at enrollment.

This study uses the World Health Organization (WHO) growth standards for inclusion criteria and the primary outcome, BMI z-score (<https://www.who.int/childgrowth/standards/en/>).

- Parent commitment to participate in 18-month study
- Plans to attend scheduled WCV and recommended follow-up WCV in 12 months
- No plans to move or change health systems in 2 years
- Parent age \geq 18 years
- Parent is English-speaking
- Household is considered lower-income (i.e., eligible for or receiving Special Supplemental Nutrition Program for Women, Infants and Children [WIC], Supplemental Nutrition Assistance Program [SNAP], Temporary Assistance for Needy Families [TANF], Medicaid, or Children's Health Insurance Program [CHIP]), screens positive for food insecurity, National School Lunch or Breakfast participation, has picked up school lunch or breakfast at curbside during coronavirus, or has experienced job disruption due to coronavirus.

Child exclusion criteria include:

- Children who attend their regularly scheduled WCV via telemedicine
- Another child in family is participating
- Pre-existing medical exclusions (cancer, type 1 diabetes, major developmental delays such as autism)
- Parents with self-reported major depression will be excluded
-

Potentially eligible child patients will be initially screened and identified using an Electronic Health Record query for patients meeting the study inclusion/exclusion criteria. Potentially eligible participants will also be screened in-person when they present at clinic for care; by

phone interview if the child has a scheduled well child visit but does not have an established history in the electronic health record (e.g., new patient); or online self-screening initiated by the parent/guardian (i.e., in response to seeing recruitment flyer, MyGeisinger message, social media ad, etc.).

Participant Enrollment

Table 1. Projected Enrollment

1. Estimated number of potentially eligible study participants (determined by Electronic Health Record):	5,438
2. Total number of study participants expected to be screened:	5,438
3. Total number of study participants expected to be eligible of those screened:	3,643
4. Target sample size (use same number stated in milestones):	2,025

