take into account the clustered nature of the study design. To test the Aim 1 hypothesis that participants will have a lower change in BMIz (and secondarily, changes in BMI, BMI50, BMIz extended) in Arms 2 and 3, as compared to Arm 1, mixed linear models^{106,107} with restricted maximum likelihood estimation will be fit. The models will include a random effect for PCPs and will be assumed to follow a Gaussian distribution. These analyses will adjust for the stratification factors used in the randomization scheme and any baseline variables found to vary across intervention arms as identified above. Contrast statements will be written as functions of the estimated regression coefficients to estimate the effect of the interventions compared to standard WCV using a two-sided alpha of 0.025 to account for multiple testing. Model assumptions will be examined (e.g., QQ plots to assess normally distributed residuals) and of the underlying Gaussian random effect distribution. Secondary analyses will estimate the effectiveness of the interventions on the percent of children overweight and obese (≥ 85 percentile of BMI and ≥ 95 percentile of BMI) at 12 months. A similar strategy will be employed using a generalized linear mixed model assuming a binomial distribution for the outcomes. These models will treat the binary outcomes as measured from the 12-month visit. Analysis of secondary outcomes in Aims 1b and 1c (involvement in preventive care, parent and home factors) will follow the same strategy as described above. Due to lagging enrollment, the study modified data collection for secondary outcome in specific aim 1b- involvement in preventive care- just after 50% enrollment was reached. The timing of this outcome measure was changed from pre-visit only to pre- or -post visit to allow for families to enroll and complete baseline data collection after a completed WCV. As there are complementary analysis methods for cluster randomized trials, we will also fit Bayesian random effect models¹⁰⁸⁻¹¹⁰ for continuous and binary outcomes. Each model will use an inverse gamma prior for the cluster random effect variance parameter.¹¹¹ We will note any differences in the effect estimates across methods.

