nonresponse to study questionnaire items. We anticipate that no more than 7% of randomized subjects will not receive allocated treatment and 10% of randomized subjects will fail to complete the study;^{63,90,115} but reasons for loss at point of WCV care and dropout will be documented. Before proceeding with primary analyses, we will characterize patterns of missingness using exploratory analyses to provide insights into how to handle the missing data. Participants with missing data will be compared to participants with complete data to ensure there are no differences. Depending on the amount of missing data, we will use a non-parametric missing data imputation method based on random forests.¹¹⁶ This method has been shown to perform as well as or better than more traditional methods of imputation, and it has the advantage of imputing both continuous and categorical data. By using random forests, we can capture non-linear relationships and interactions present in the dataset that may otherwise be missed when using a different method. At least 5 complete datasets will be created and combined using the methods of Rubin.¹¹⁷

Heterogeneity of treatment effect (HTE). HTE analyses are incorporated into Aim 2 when examining moderator effects. Additional sub-group analyses will be performed by child sex (males, females) and baseline BMI weight category (overweight, obese). These sub-group analyses will employ the same models as described in Aim 2.

Aim 3. The **RE-AIM framework**²⁹ will be used to evaluate the interventions' reach to the target population and subgroups (e.g., by provider type, those with food insecurity and hunger), comparative effectiveness, adoption by PCPs, implementation fidelity and barriers, and maintenance of intervention components over time, so as to inform translation of this study into practice.

EXPECTED RISKS/ BENEFITS

Potential Risks

The greatest potential risk to participants in this research is a loss of confidentiality. To minimize the risk of loss of confidentiality, all data collected as part of this study will be stored on the Geisinger password-protected network only accessible to IRB-approved study staff. Participants will also be assigned a unique study ID for data collection. In the event that any data would be shared outside of Geisinger, it would be done using an IT-approved secure transport method to ensure data security is maintained.

Benefits

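### The 12-month overweight and obesity outcomes pool new cases with children already above the cut-off at entry, so an effect on new obesity is diluted and no outcome isolates it

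*Combined protocol and SAP*

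**What the plan says.** - **Objective.** Specific aim 1 compares the arms "on obesity prevention for preschool-aged children from rural, lower income households with BMI-for-age and -sex > 50th percentile at baseline". Research Design likewise describes effectiveness "on the prevention of obesity among preschool-aged children (Aim 1").
- **Eligibility.** Under Study Population, a child is "eligible if greater than or equal to 50th percentile for BMI-for-age and -sex at any visit (WCV, acute, etc".) within a look-back window or at enrollment. No upper BMI limit is given, and the child exclusion criteria do not mention existing overweight or obesity.
- **Binary outcomes.** Aim 1a looks at effects "on the percent of children overweight (> 85th percentile BMI-for-age and -sex) and obese" at one year. The Aim 1 paragraph of the Analytic Plan fits a binomial mixed model and adds: "These models will treat the binary outcomes as measured from the 12-month visit". The Outcomes section says the categories follow CDC definitions.
- **Adjustment.** Models adjust for the stratification factors and for baseline variables that differ between arms, defined as a standardized difference above 0.10. Baseline BMI is among the variables compared. Appendix B, item 21, lists baseline BMI category as a covariate, but the Analytic Plan does not require it in every model.
- **Subgroups.** The HTE paragraph plans analyses by "baseline BMI weight category (overweight, obese"), using the Aim 2 models, whose main outcome is change in BMIz. Appendix C (Effectiveness) mentions robustness across subgroups, including child baseline weight status.

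**The concern.** A child obese at both visits and a child who became obese count the same in the planned percentages. Prevention concerns only the second child. The Outcomes section adds these percentages because BMIz may mean little to parents and clinicians, and it wants to tell parents what to expect. A parent whose child is not obese wants the chance of becoming obese, and the pooled percentage does not give it.

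Two things follow. First, an intervention that acts on new onset is diluted by persistent cases, so a real effect may be hard to see. Second, 12-month prevalence depends heavily on who was obese at entry. If baseline weight status enters the model only past a threshold, smaller imbalances between arms pass straight into the result.

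**Working it through.** **The plan's own figures.** The documents size the trial for BMIz only. For d = 0.20, two-sided alpha 0.025 and 80% power: 2 × ((2.2414 + 0.8416)/0.20)² = 475.2, or 476 per arm. With 28 families per PCP, ICC 0.005 and COV 0.25, the design effect is 1 + ((1 + 0.25²) × 28 − 1) × 0.005 = 1.144, and 475.2 × 1.144 = 544, met by 28 × 20 = 560. Then 560/(1 − 0.17) = 675. Both stated figures reproduce. After 10% dropout, 675 × 0.90 = 607 per arm are available, which is used below. No power, baseline obesity share or onset rate is stated for the binary outcomes.

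**Assumed inputs.**
- b, share obese at entry: 0.20-0.28, from the 13.9% national preschool prevalence in Background and Rationale, concentrated in the upper 70% to 50% of the BMI distribution (13.9/0.70 = 19.9%; 13.9/0.50 = 27.8%). A low case of 0.10 uses the reference 5% over 50%.
- s, persistence at 12 months: 0.60-0.90. Background and Rationale says "60 to 90 percent of preschool-aged children with obesity had persistent obesity into adolescence" and adulthood. That horizon is much longer than a year, so its use here is an assumption.
- i, yearly onset among children not obese at entry: 0.03-0.06, assumed.
- Effect: onset cut by 25%, persistence unchanged. Clustering is ignored below.

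**Formulas.** Prevalence P = b·s + (1 − b)·i. Persistent share = b·s/P. Change in prevalence = (1 − b)·i × 0.25.

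| b | s | i | P | Persistent share | Change in P |
|---|---|---|---|---|---|
| 0.20 | 0.60 | 0.06 | 0.120 + 0.048 = 0.168 | 71% | 1.2 points |
| 0.28 | 0.90 | 0.03 | 0.252 + 0.0216 = 0.274 | 92% | 0.54 points |
| 0.10 | 0.60 | 0.06 | 0.060 + 0.054 = 0.114 | 53% | 1.35 points |
| 0.10 | 0.90 | 0.03 | 0.090 + 0.027 = 0.117 | 77% | 0.68 points |

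For b = 0.20-0.28 the prevalence odds ratio is 0.92-0.97.

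**How far the inputs matter.** Persistent cases are the majority only while i < b·s/(1 − b): below 6.7% a year at b = 0.10, s = 0.60, and below 15% at b = 0.20, s = 0.60. Over b = 0.10-0.278, s = 0.60-0.90 and i = 0.02-0.15, the persistent share runs from 31% to 95%. For overweight the documents give no persistence figure, so no share is claimed.

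**Signal for each contrast.** At b = 0.20, s = 0.60, i = 0.06:
- Prevalence, 0.168 against 0.156: SE = √((0.1398 + 0.1317)/607) = 0.0211; z = 0.012/0.0211 = 0.57.
- Incidence, 0.060 against 0.045 in 607 × 0.80 = 486 per arm: SE = √((0.0564 + 0.0430)/486) = 0.0143; z = 0.015/0.0143 = 1.05.

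The ratio is 1.9 here and reaches 3.3 at b = 0.28, s = 0.90, i = 0.03. Stratifying the prevalence contrast on baseline obesity lowers the range to about 1.2-2.2. Incidence z runs from 0.69 to 1.05, which is 6-12% power at two-sided 0.025.

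**Imbalance the rule leaves alone.** A standardized difference of 0.10 is a difference of 0.10 × √(b(1 − b)) in baseline obesity: 4.0 points at b = 0.20, 4.5 at b = 0.28. Multiplied by (s − i), the shift in 12-month prevalence is 0.040 × 0.54 = 2.2 points up to 0.0449 × 0.87 = 3.9 points, against a prevention effect of 0.54-1.2 points.

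**The case against.** The plan already goes some way. Appendix C intends to examine effectiveness by child baseline weight status, and 12-month obesity among children not obese at entry is new obesity. That stands in part: it is an intention without a model or outcome attached. The HTE paragraph, which does name models, lists only the overweight and obese strata. The group below the 85th percentile, where all new overweight arises, is missing.

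A reader might infer that these outcomes cannot show prevention. The documents do not support that. In randomised arms, fewer new cases lower 12-month prevalence; persistence dilutes the contrast but does not bias it. Nor do they support saying that the outcomes mostly measure persistence as a fact, because baseline share, 12-month persistence and onset are all unstated.

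A reader might also infer that baseline imbalance is ignored. It is not: differences above 0.10 lead to adjustment. The gap is below the threshold. Chance imbalance of that size is also random error that the unadjusted standard error already allows for, so the gain from always adjusting lies in precision, interpretation and a model fixed in advance.

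The advantage of incidence is conditional too. It assumes no effect on children already obese, although Arms 2 and 3 offer the screening tool to all. Under the 20-28% inputs, a relative cut in persistence of only 5-8% makes the unadjusted prevalence contrast as strong. With 6-12% power, incidence is no rescue, and a reader should not conclude that it ought to lead while prevalence becomes descriptive. Finally, the Outcomes section ties prevention to the primary BMIz change, so no primary conclusion rests on these percentages.

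**Conclusion.** The point holds as one of dilution and interpretation in secondary outcomes. The objective is prevention, children already above the cut-offs are enrolled, the binary outcomes are status at 12 months, and no new-onset outcome is specified; none of this depends on assumed figures. That persistent cases probably dominate 12-month obesity does depend on them: 71-92% with 20-28% obese at entry and 53-77% with 10%, at 60-90% persistence and 3-6% onset, and down to 31% with few obese at entry and high onset. Under the 20-28% inputs, a 25% fall in new obesity appears as 0.5-1.2 points of prevalence, while an imbalance just inside the plan's tolerance could move prevalence by 2.2-3.9 points. The primary analysis is not affected.

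**What to change.** In Aim 1a and the Aim 1 paragraph of the Analytic Plan:

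1. Add two secondary outcomes: (a) obesity at 12 months among children below the 95th percentile at the baseline WCV; (b) overweight or obesity at 12 months among children below the 85th percentile at the baseline WCV. Use the binomial mixed model already planned and one stated growth reference at both visits, since the plan uses WHO standards for eligibility and BMIz but CDC definitions for the categories.
2. Report remission among children obese at baseline separately.
3. Keep the all-participant 12-month comparison, and always adjust it for baseline BMI or weight category, whatever the observed imbalance.

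The cost is plan wording and a few more models on BMI values the plan already uses. The incidence models have fewer children and few events, so their intervals will be wide and should be read as estimates rather than tests.

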During the start-up of the study we will develop a formal Data Management Plan to document how data will be collected, organized, stored, as well as a statistical analysis plan. Descriptive statistics will include evaluation of all data for underlying distribution and summary statistics, using means with standard deviations and medians with interquartile range for continuous variables, and frequency with percentages for categorical variables. The data will be summarized for all patients enrolled and will be stratified by randomization arm and study time point. We will assess the quality of data, evaluating outliers and patterns of missing data using graphs such as histograms and stem-and-leaf plots. Bi-variate analyses will be used to assess differences in patients (e.g., parent BMI, child biological sex, baseline BMI) between randomization arms. Since it is not recommended to perform inferential statistics to assess balance of baseline participant, family, community, and physician factors in a randomized study, we will use standardized differences.¹⁰³ Any standardized difference > 0.10 will be considered unbalanced and, thus, a potential confounding variable. We will also follow the CONSORT¹⁰⁴ extension to cluster randomized trials when reporting results.

As data is collected from participants as part of this research study, in an effort to facilitate additional analyses, the Geisinger study team plans to share a de-identified data set with PSU. This data set will be shared utilizing Geisinger IT-approved methodologies (Secure Transport, e-secure, etc.) to ensure that patient data is protected. These data will be stored at PSU in a secure network location that is only accessible to PSU study staff. These analyses will assist in exploring additional study research questions that may arise.

Aim 1. The primary outcome variable is change in BMIz at 12 months. BMIz is the most widely used obesity-related outcome per systematic review and thus was chosen for comparability with prior literature.^{11,105} The primary analysis will follow the “intention-to-treat” principal. That is, all participants enrolled will be analyzed according to their group assignment at the point of care (WCV) regardless of intervention received and compliance. Analyses will

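### The Aim 1b baseline involvement score may be taken after the intervention visit, with no rule keeping it out of the analysis; the Aim 2a parent mediator scale is timed at baseline only

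*Combined protocol and SAP*

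**What the plan says.** **Timing of the Aim 1b measure.** The Analytic Plan (Aim 1) places a change to data collection "just after 50% enrollment was reached" and gives slow recruitment as the reason. On the measure itself it states: "The timing of this outcome measure was changed from pre-visit only to pre- or -post visit to allow for families to enroll". The purpose it gives extends to letting those families "complete baseline data collection after a completed WCV". Appendix B, Table 4, row 11 (Perceived Involvement in Care) agrees: its baseline may be before or after the WCV, and a follow-up score is also scheduled. The row describes a parent's rating of involvement in the clinical encounter, adapted for the WCV.

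**Analysis of Aim 1b.** It "will follow the same strategy as described above". What stands above is of two kinds. BMIz is analysed as a change, and so, secondarily, are "changes in BMI, BMI50, BMIz extended". For overweight and obesity, "These models will treat the binary outcomes as measured from the 12-month visit". The models also adjust for "any baseline variables found to vary across intervention arms as identified above", and the trigger is set earlier in the Analytic Plan: "Any standardized difference > 0.10 will be considered unbalanced and, thus, a potential confounding variable".

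**Other statements on timing.** The Source note to Table 4 places study-questionnaire variables, which include rows 11 and 14, after the baseline WCV. The Timing note defines baseline as around enrollment. Study Procedures allows recruitment up to 6 months before the visit or after it.

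**Aim 2a.** Row 14 (parent attitudes, norms, perceived control and intention) is labelled Mediator and timed at baseline only. The Analytic Plan (Aim 2) requires a mediator to lie on the causal path from intervention to outcome.

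**The concern.** Before the visit, a parent can only rate earlier care. After it, a parent in Arm 2 or 3 rates the encounter that the intervention was meant to change. Table 4 calls both answers baseline. If the second kind is subtracted from the 12-month score, or used as a covariate, part of the treatment effect is removed. The amount depends on how many families answered after the visit, so a reader could not tell a diluted contrast from a weak intervention.

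For Aim 2a the difficulty runs the other way: the early answers are the problem. A response given before any exposure cannot transmit the intervention's effect, and row 14 has no later measurement to use instead. Such answers could be reported as mediators.

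**Working it through.** **1. The plan's own figures.** The documents give no effect size, variance or power for Aim 1b or 2a. The figures that can be checked are the parent item totals in Appendix B against the rows of Table 4.

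- Baseline: 14+6+20+9+25+28+13+16+4+9+12 = 156 (stated 156).
- 6 months: 9+28+13+16+4+9 = 79 (stated 79).
- Follow-up: 6+20+9+28+13+16+4+9+12 = 117 (stated 97).

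The gap is 20 items. Two sets of whole rows add to 20: row 11 alone (20), or rows 17 and 18 together (16 + 4). The total therefore leaves open whether the involvement scale is on the 12-month form.

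**2. Change score.** Let f be the share of families whose baseline is post-visit, equal across arms, and g the index-visit effect divided by the 12-month effect. The baseline gap between arms is fg times the 12-month effect, so a change score retains 1 − fg. Both inputs are assumed.

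| f | g | retained |
|---|---|---|
| 0.10 | 0.25 | 97.5% |
| 0.25 | 0.5 | 87.5% |
| 0.5 | 1 | 50% |

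f is about 0.5 if the first half of families all answered before the visit and every later family answered after it. It is lower if pre-visit recruitment continued to supply many of the later families. If the Source note is right, f approaches 1 and the retained share approaches 1 − g. Nor is g bounded by 1, since a score taken just after the visit may show a larger effect than one a year later.

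**3. Adjustment through the 0.10 rule.** If the partly post-visit score is always a covariate, with baseline to 12-month correlation r, the retained share is about 1 − rfg. At r = 0.5 this is 1 − 0.5×0.25×0.5 = 94% and 1 − 0.5×0.5×1 = 75%. When adjustment occurs only if some pair of arms differs by more than 0.10, simulation gives about 96% and 79% for the same two settings. With r from 0.3 to 0.7 the second figure runs from about 87% to 70%. The simulation used three arms of 20 PCPs with 28 families each, an effect of 0.20 SD and ICC 0.005. Those are the BMIz planning inputs, so the results are illustrations for this scale.

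**4. Unadjusted 12-month score.** The baseline value does not enter, so 100% is retained.

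**5. Row 14 against the mediator definition.** Baseline may fall up to 6 months before the WCV. For portal users in Arms 2 and 3 the FNPA opens 14 days before the visit (Study Procedures), so exposure can begin before the WCV itself. An answer given before both the FNPA release and the WCV precedes all exposure and fails the plan's own definition. An answer between the two may not. That row 14 may also be collected after the visit is an inference from "complete baseline data collection after a completed WCV"; the stated change names only Aim 1b.

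**The case against.** The best defence is that the harmless reading is the natural one. Aim 1b, unlike Aim 1a, does not speak of change. Row 11 is labelled a secondary outcome, while Table 4 marks its covariates explicitly. The 12-month binary outcomes also stand closer in the text than the change scores. This favours the 12-month score but does not commit to it: the cross-reference covers both kinds of outcome, and the 0.10 rule applies to any baseline variable.

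For Aim 2a, the plan carries forward only variables associated with both intervention and BMIz. Under randomization a truly pre-exposure score should pass the first test mainly by chance, and Sample Size and Power calls Aim 2 descriptive. Both points reduce the problem; neither makes an early answer a mediator.

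The in-clinic pilot described post-visit consent and baseline questionnaires, but it covered fewer than 5 sites and was discontinued. It also meant to capture attitudes before the visit. It says little about the main sample.

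Several stronger readings are tempting and unsupported:

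- **The Aim 1b effect is halved.** The documents give neither f nor g and do not choose the outcome form.
- **Half is the worst case.** The Source note allows a larger f.
- **Row 11 was left off the 12-month form.** Rows 17 and 18 fit the item gap equally well.
- **Any answer dated before the WCV is free of exposure.** FNPA release may come first.
- **The whole of Aim 2a fails.** The PCP scale (row 9) is also measured at follow-up and 24 months.

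**Conclusion.** The point holds for one secondary outcome and for the parent half of one descriptive aim. Following the plan as written can subtract or adjust for a score that the intervention has already moved, and can present pre-exposure answers as mediators. Both should be settled before analysis.

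The text supports the direction: when index-visit and 12-month effects have the same sign, the Aim 1b contrast is pulled towards no effect under a change score, less so under triggered adjustment, and not at all under an unadjusted 12-month score. The size is unknown, because f, g and the correlation are all assumptions.

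A reader might infer that the primary result is compromised. The documents do not support that: BMIz comes from recorded height and weight, supplemented by parent report of those measures, and does not use this scale. The only route in is the 0.10 rule admitting a post-visit questionnaire score as a covariate.

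**What to change.** **(a) Aim 1b outcome.** State that it is the 12-month involvement score in the same mixed model (PCP random effect, stratification factors), with no baseline involvement term in the main model. Never subtract or adjust for post-WCV scores, and exclude them from the 0.10 balance rule.

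**(b) Timing variable.** Derive questionnaire date minus WCV date for every family. Report the post-WCV share and the post-WCV scores by arm. As a sensitivity analysis only, adjust for baselines dated before the WCV and, in Arms 2 and 3, before the FNPA was released to the parent. State that this timing is fixed after PCP randomization and may differ by arm.

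**(c) Timing text.** Reconcile the pre-visit-only statement in the Analytic Plan with the Source note to Table 4.

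**(d) Row 14.** Do not report answers dated before exposure (FNPA release or WCV) as mediators; use them as baseline moderators or covariates. Keep later answers as exploratory mediators, stating that they have no baseline value. If few exist, say that the parent half of Aim 2a cannot be answered.

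**(e) Item total.** Reconcile 117 with 97 and confirm that row 11 is on the 12-month form. If it is not, state that Aim 1b has no 12-month involvement score.

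**Cost.** Wording in the promised statistical analysis plan, one derived variable and one corrected entry. The main Aim 1b model drops no family on account of baseline timing and needs no new data if row 11 is on the form; it gives up whatever precision a genuine baseline would have added. The date-defined subset has a standard error larger by about 1/√(1 − share excluded): 1.15 times at 25% excluded and 1.41 times at 50%. If row 11 is not on the form, the Aim 1b claim shrinks.
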